
in the small space of the scanner. These individuals will have the opportunity to terminate the scan session. Furthermore, all recruits will be screened for phobias prior to enrollment. There is a medical technologist at the imaging site at all times to insure scanner safety, and neuroradiologists on call as needed. If an abnormality is noted on the structural MRIs by study staff, the PI will provide the participant with a copy of the scan and encourage them to follow up with a neurologist.

Protection against risks associated with neurocognitive tests. The neurocognitive assessments have minimal risk associated with them. Some participants experience stress associated with being tested, though this tends to be quite limited. Breaks will be given in those cases. Research staff that collect data have been trained in the conduct of all cognitive function tests by other senior staff members. Research staff members will be certified in the conduct of the cognitive function tests before they work with study participants.

Data and Safety Monitoring Plan:

The research team will follow the procedures for data safety and monitoring as required by the Institutional Review Board at the University of Florida (UF IRB). The research team will monitor participants for any potential adverse events, and all reported events will be forwarded by the PI to the UF IRB.

A data and safety monitoring plan (DSMP) has been implemented to ensure the safety of all participants involved in the study and to ensure the validity and integrity of the data. The primary goal of the DSMP will be to monitor the progress of the study and safety of participants and if necessary, recommend modifying the study or terminating the study as appropriate.

- The PI's will be responsible for coordinating activities of the DSMP, including:
 - Lab Meetings twice per month, to discuss participant involvement in the study, and any issues that have developed or need revision
 - Safety concerns
 - Data Storage and safety
 - Participant safety
 - Outcome data
 - Data quality
 - Integrity
 - Intervention efficacy
 - Recruitment
 - Performance

Both the PI and the study staff will review and examine reports of adverse incidents immediately, and make reports to the IRB as necessary for any and all of the following situations:

- Serious and non-serious adverse events that may occur
- Suspicion of scientific fraud or misconduct
- Any other issues which may warrant protocol changes or modifications.

Procedure for collection and storage of data. A number of quality control procedures will be used to ensure the validity and integrity of the data and the safety of all participants involved in the study. Relevant data and safety information obtained on each study participant will be verified against the original source documents by the primary study coordinator and any

identified discrepancies will be reviewed at these meetings. The primary goal of these meetings will be to monitor the progress of the study and safety of participants and if necessary, recommend modifying the study or terminating the study as appropriate.

All identifying information will be archived in [name] and [name] neuroimaging laboratory within the Center for Cognitive Aging and Memory. Imaging data will undergo several levels of processing, and all raw and processed data will be archived on a University password-protected server in password-protected folders and files. Only study staff will have access to these files. The self-report data will be double entered using the RedCap Data System. This system signals the user when an out-of-range value is entered. All data entry is then verified via double-entry, with the program signaling mismatches with the original entry. Next, computer-generated reports of variable frequencies and subject lists will be reviewed, leading to possible corrections to coding or entry. After checking for accuracy of data within a given group, data will be stored in the password-protected folders along with the imaging data.

Location and logistics of data collection. All procedures involving human subjects will be performed at facilities of the UF Health Care System. Neurocognitive testing and training will be performed at the clinical research unit of the Center for Cognitive Aging and Memory with an ancillary location at the Village at Gainesville. Several clinical research examination rooms are equipped and dedicated to neurocognitive and functional assessment, and contain all necessary computers and test materials. Storage of neuroimaging data backup will occur at the CAM Neuroimaging Laboratory. Neuroimaging will take place at the AMRIS facility of the McKnight Brain Institute.

Sharing of data from collaborating sites. Due to the multi-center design of the study, data will be shared with the University of Florida from a collaborating site, the University of Arizona. The collaborating site will send fully de-identified data. Data transfer will take place using the secured infrastructure of the University of Florida RedCap system for questionnaire data. De-identified raw neuroimaging data will be transferred to UF using the Secure File Transfer Protocol (SFTP) onto UF Dropbox servers. A data confidentiality agreement will be signed and filed with the UF IRB before any data are collected at any site.

Storage of collected data. All electronic data are stored in password protected, secured computer systems. All paper data will be stored in a locked file cabinet. Data will only be removed when coded, entered, or audited. Only the participant's study identification number will appear on any data forms. Only the PI, the Co-Is, and the RAs will have access to the completed data forms and electronically stored data. All data are considered part of the participant's confidential record. Data collected from research participants will be stored in a secured, password protected computer file that is separate from network systems. All paper data (e.g., subject contact information, consent forms, etc.) will be placed in a locked file cabinet within 24 hours of their acquisition as designated by the study's RA. All data will remain confidential. Data entry requirements. The data entry system will require a login identification and password in order to gain access to the data. Where appropriate, validation and range rules will be applied to the actual entry fields. Only the PI and Co-Is will be able to view the data in its raw state.

Audit/verification of entered data. All data designated as primary outcome data will be subject to a 100% cross-referencing between electronic and paper forms. This audit must have an error rate less than 1%. If the verification fails the audit, all data will be re-entered, the original computer files discarded, and the newly re-entered data audited. This process will continue until the audit no longer exceeds the maximum allowable error rate. All audits will be supervised and documented by the PI.

Data management and analysis. Our research team has substantial experience in the design and implementation of data management procedures that provide accurate recording and storage of data, participant confidentiality, and timely analysis. Based on our past experience, we believe that our major data management and analysis needs for the proposed project can be met by using a high-end PC, equipped with the latest version of SPSS for Windows and appropriate spreadsheet programs. All data files are automatically backed-up daily.

Data quality control. All staff involved in data collection will be trained and certified to ensure their competence, and re-certified periodically throughout the study as we have done in similar trials. Data will be collected and numerically coded using pre-tested electronic entry forms. At the time of collection, there will be initial clerical review of all data for accuracy and completeness. Every effort will be made to ensure that missing data are kept to a minimum. Data entry programs with range checking and response validation will be used for all data entered. Under supervision from the PI, the data manager will conduct error checking procedures and preliminary analyses on all data to ensure their accuracy. The RAs will be trained to avoid omissions in data entry and computer entry protocols will be programmed to avoid accidental skipping of question items. We believe that the quality control system to be used will ensure a complete and accurate database, and maximize the likelihood that the intervention will be delivered correctly and efficiently. As we have done in prior studies, a manual of procedures will be developed during the initial study start-up period that explicitly describes the specific procedures related to intervention delivery, data collection, and quality assurance.

Frequency of data review. Relevant data and safety information obtained on each study participant will be verified against the original source documents by the primary study coordinator on a bi-weekly basis. As noted above, any identified discrepancies will be discussed with the Principal Investigator and reviewed at weekly meetings.

Measurement and reporting of participant accrual and adherence to eligibility criteria. Review of the rate of participant accrual, adherence to inclusion/exclusion criteria will occur weekly during the recruitment phase and then every month to assure that participants meet eligibility criteria and ethnic diversity goals outlined in the grant proposal.

Safety Review Plan Study progress and safety will be reviewed twice per month (and more frequently if needed) by the principal investigator. An annual report will be compiled and will include a list and summary of AEs. In addition, the annual report will address (1) whether adverse event rates are consistent with pre-study assumptions; (2) reason for dropouts from the study; (3) whether all participants met entry criteria; (4) whether continuation of the study is justified on the basis that additional data are needed to accomplish the stated aims of the study; and (5) conditions whereby the study might be terminated prematurely. The IRB and other applicable recipients will review progress of this study annually.

Final storage of paper data. All paper data (e.g., consent forms) may be scanned, and will finally be housed at a facility that specializes in the storage of medical/ research information. The destruction date of these files will be at least 7 years from the termination of the study and will be authorized by the Principal Investigator of the research study.

Access to cleaned computer data. Once the study is complete, and all data have been collected, entered and passed the audit process, the data will be available to the Principal Investigator and his designates for analysis. Only the Principal Investigator can give permission for the release of aggregated study data. No confidential information may be released without

the express written consent of the study participants. Only copies of the finalized data will be released. The original data file will remain in its pristine state.

Description of plan for safety monitoring. Protection of participants from risks related to the study is of paramount concern.

Monitoring physical health and safety. All assessment visits will be conducted at a central location and all testing sessions will be conducted and supervised by a trained and certified research staff that will monitor potential adverse experiences and symptoms. At each visit, participants will be asked to report any adverse events they have experienced since their last visit. Immediate medical treatment will be provided for any illness or injury resulting from this study. Trained nursing staff members are present in the research center at all times, and a physician will also be available to evaluate the participant if needed.

In addition to the assessments conducted at in-person study visits, participants will be asked about any adverse events, including itching, pain, nausea, headache, etc. they have had. Participants will also be asked about their mood, including depressive symptomatology, and other health related activities (i.e., physical activity), as well as general health status. Based on reported symptoms, participants may be asked to come in for an additional follow-up assessment visit with one of the healthcare professionals on the study team (i.e., physician or psychologist) for further evaluation of their symptoms. Based on information obtained at this visit, participants will then be referred for follow-up assessment and/or treatment with the appropriate healthcare provider.

Monitoring mental health and safety. Any participant who endorses clinical levels of any psychiatric disorder or who endorses suicidality will be referred to [name], study psychologist, for further follow-up assessment. The psychologist will then provide a recommendation regarding the appropriate course of follow-up and also advise on whether it is safe for the participant to continue in the study. If a participant is found to be actively suicidal with a plan and/or intent, they will be escorted immediately to the emergency room at the Shands Hospital at the University of Florida. If safety is an issue, UF security or local authorities will be called for assistance.

Data and Safety Monitoring Board (DSMB):

A **Data Safety Monitoring Board (DSMB)** is established, with responsibility to monitor all aspects of the study, including those that require access to any masked data. The DSMB and its chair are named and approved by the NIA. It is planned that the DSMB meets by conference call as determined by the DSMB and the NIA. The DSMB has access to all deidentified study data, documents and progress. The Intervention and Safety Committee, **comprised of safety personnel from each site, the Chair, and a representative of the DMAQC** reports to the DSMB for issues related to participant safety.

The DSMB has the following charges:

- Review the study protocol.
- Review data (including masked data) over the course of the trial.
- Identify problems relating to safety over the course of the study.
- Identify needs for additional data relevant to safety issues and request these data from the study investigators.
- Propose appropriate analyses and periodically review developing data on safety and endpoints.
- Make recommendations regarding recruitment, treatment effects, retention, compliance, safety issues and continuation of the study.

- At any time, the DSMB may recommend discontinuation of any component/treatment group of the study

Finally, the NIA makes the final decision on whether or not to accept the DSMB's recommendation about discontinuation of any component of the study. Any serious adverse event that might be due to the study intervention are reported to the DSMB, the IRBs, and to the NIA Project Office. The exact timeline for reporting serious adverse events is determined by the DSMB, IRBs, and NIA.

8. Possible Benefits:

There are well-documented benefits for older adults who participate in cognitive training, including improvement in working memory, attention, and executive functions. Deficits in these cognitive abilities significantly impact quality of life, financial capacity, medication adherence, and mortality in older adults. Those participants randomly assigned to the CT groups may benefit from these effects. Participants assigned to the Education Training Control group may obtain better knowledge about educational facts from the videos, but are unlikely to have the same benefits as those in the CT group. Those participants randomly assigned to the tDCS+CT treatment group may experience further benefit beyond that of cognitive training alone. Benefits to society will include the contribution of novel data regarding the efficacy of neuromodulation methods for enhancing cognitive training effects in older adults. This may help inform treatment protocols in a growing segment of the US population (i.e., those 65 years and older). Data collected from this study will serve as a foundation for larger clinical studies that examine optimized methods for treating aging-related cognitive decline using cognitive training and tDCS. Some participants may not benefit from the study at all.

9. Conflict of Interest:

None

1. Sumner P, [name] RA, Bompas A, Evans CJ, Singh KD. More GABA, less distraction: a neurochemical predictor of motor decision speed. *Nat Neurosci.* Jul 2010;13(7):825-827.
3. [name] RA, Muthukumaraswamy SD, Freeman TC, Singh KD. Orientation discrimination performance is predicted by GABA concentration and gamma oscillation frequency in human primary visual cortex. *J Neurosci.* Dec 16 2009;29(50):15721-15726.
4. Puts NA, [name] RA, Evans CJ, McGlone F, McGonigle DJ. Regionally specific human GABA concentration correlates with tactile discrimination thresholds. *J Neurosci.* Nov 16 2011;31(46):16556-16560.
5. Gao F, [name] RA, Li M, et al. Edited magnetic resonance spectroscopy detects an age-related decline in brain GABA levels. *Neuroimage.* Sep 2013;78:75-82.

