To date, all prior trials of tDCS have applied a fixed dosing strategy (e.g., 2mA for 20 min with electrodes at F3/F4 [10-20 measurement system]) in attempts to enhance CT – including ACT. However, prior research demonstrates that individual variability in head and brain anatomy (e.g., degree of atrophy, skull thickness, etc.) significantly alters the spread and intensity of direct electrical current delivered to the brain person to person. The impact of individual variation in electrical current delivered to the brain for clinical outcomes has rarely been examined, and methods aimed at increasing stimulation effectiveness and optimizing readiness to learn are only now beginning to be explored. We will use advanced MRI-derived computational modeling of electrical current from existing MRIs to provide a means for accurately estimating individual differences in tDCS current delivery to the brain in the largest existing sample of participants undergoing tDCS (i.e., ACT) with multimodal neuroimaging data. When combined with state-of-the-art machine learning approaches and behavioral outcome data (only unblinded once ACT has completed all follow-up visits), precision models of tDCS current will be derived to identify critical stimulation dosing characteristics (e.g., current intensity, direction/path of current) in specific brain regions associated with response vs. non-response to tDCS and CT intervention. These data will not only provide much needed information for determining how individual participant characteristics impact tDCS efficacy, but will also serve as a foundation for future precision medicine applications of tDCS and CT to remediate cognitive decline in older adults and potentially prevent or alter the trajectory towards Alzheimer's disease.

Aim 1. Determine inter-individual variability in tDCS current distribution using MRI-derived finite element modeling.

H1.1. Variability in neuroanatomy (e.g. increased atrophy, sulcus depth, skull thickness, etc.) will significantly decrease current intensity and alter the pathway/direction of electrical current flow induced by tDCS in the brain.

H1.2. White matter lesions, as measured by white matter hyper-intensities on FLAIR imaging, will significantly decrease current intensity and significantly alter the direction of electrical current flow induced by tDCS.

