Aim 2. Determine critical tDCS current properties and specific brain regions associated with responder vs. non-responder to tDCS and CT intervention using machine learning.

H2.1. Current intensity and direction will significantly predict response vs. non-response to tDCS and CT intervention on the NIH Toolbox Fluid Cognition Composite Score (ACT primary outcome).

H2.2. Current intensity and direction within bilateral rostral middle frontal, right superior frontal and frontal pole, and left pars orbitalis regions will most strongly predict response vs. non-response to tDCS and CT intervention.

H2.3. Current intensity and direction will outperform clinical/demographic characteristics alone (e.g., age, sex, comorbidities, mental health, Alzheimer's disease risk, cognition, etc.) in predicting tDCS response.

Exploratory Aim. Evaluate computational methods for achieving precision delivery of dosing characteristics in tDCS.

HE.1. Adjusting tDCS current intensity input into computational models will achieve precision delivery of targeted dosing characteristics.

HE.2. Adjusting electrode locations input into computational models will achieve precision delivery of targeted dosing characteristics.

No new data will be collected from participants to achieve these aims. Only existing data collected with consent from participants in the course of the primary ACT study will be used. These data will be analyzed using advanced analytic methods (computational modeling and machine learning) to achieve all three aims specified in section 6.18.

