Aim 1. Dependent measures. The primary dependent measure in Aim 1 is current density computed in individual head models from existing MRIs. Current components will be further quantified as current intensity and direction. **Rationale.** Computed current density will provide an estimate of tDCS current dose within brain regions unique to each person's neuroanatomy. **Outcome analyses.** **H1.1.** The regression analysis between current density (dependent variable) and anatomical measures (independent variable) e.g., brain volume ratio, sulcus depth, bone thickness will test the hypothesis that unique current density distribution in each person is significantly affected by individual characteristics in neuroanatomy. **H1.2.** Current characteristics generated from models will be compared between inclusion and exclusion of white matter lesions. A false discovery rate (FDR)-corrected voxel-wise within participants analysis will test the hypothesis that inclusion of white matter lesions in computational models significantly alters current characteristic predictions.

Aim 2. Dependent measures. The primary dependent measure in Aim 2 is balanced accuracy. This measure provides an overall index of the performance to differentiate responders from non-responders. **Rationale.** By using this measure, we provide a single performance indicator upon which the **heterogeneity of response** in tDCS augmented CT can be revealed. Much of our preliminary data is based on analyses using this measure. **Outcome analyses.** All analyses will be conducted with the intent to optimize prediction of tDCS outcome. McNemar test at one-tailed 0.05 significance level will be conducted to determine whether current intensity and direction will outperform clinical and demographic characteristics alone in predicting tDCS response.

Exploratory Aim. Dependent measures. The primary dependent measure in the Exploratory Aim is log-likelihood distance measure. Adjustments of electric current intensity and electrodes placement in computational models will be used to minimize the log-likelihood distance measure to the Gaussian Mixture Model of the responders' current distribution.

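### Electric-field Aim 2 treats predictors of response to tDCS plus CT as tDCS dosing characteristics without specifying a CT+sham comparison

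*Combined protocol and SAP*

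**What the plan says.** Section 6.18 plans current models for all 360 participants and uses them in three steps.

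- **Aim 1** relates anatomy to current. H1.1 expects that "Variability in neuroanatomy (e.g. increased atrophy, sulcus depth, skull thickness, etc.) will significantly decrease current intensity". For H1.2, "Current characteristics generated from models will be compared between inclusion and exclusion of white matter lesions", within participants.
- **Aim 2** classifies responders and non-responders. H2.1 states that "Current intensity and direction will significantly predict response vs. non-response to tDCS and CT intervention on the NIH Toolbox Fluid Cognition Composite Score", and H2.2 adds, for the same classification, that "Current intensity and direction within bilateral rostral middle frontal, right superior frontal and frontal pole, and left pars orbitalis regions will most strongly predict" it. The measure is balanced accuracy, and "All analyses will be conducted with the intent to optimize prediction of tDCS outcome". The one test with a stated level belongs to H2.3: "McNemar test at one-tailed 0.05 significance level will be conducted to determine whether current intensity and direction will outperform clinical and demographic characteristics alone". The outcome being predicted there is response to tDCS.
- **The Exploratory Aim** adjusts modelled intensity and electrode placement to "minimize the log-likelihood distance measure to the Gaussian Mixture Model of the responders' current distribution".

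The introduction to the section gives the intended reading: "precision models of tDCS current will be derived to identify critical stimulation dosing characteristics", with the results said to bear on tDCS efficacy. The timeline paragraph says that allocation will be available for Aim 2 and the Exploratory Aim. Nowhere in 6.18 is a CT+sham comparison, an arm term or an arm-by-current interaction specified. The section gives neither a gain threshold nor a time point for responder, although Section 6.1 has assessments at baseline, after 12 weeks and at one year.

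**The concern.** Participants in the CT+tDCS arm are also scheduled for the full training programme (40 hours, Section 6.4). A responder there may have gained from training, from repeated testing, from stimulation, or from a mixture. The predictor is not an independent measure of exposure: every active participant gets the same 2 mA setting, so differences in modelled current between people come from head and brain anatomy. If anatomy also relates to how much a person gains from training or practice, current will predict response even when stimulation does nothing.

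The only named comparator does not remove this. The clinical and demographic examples under H2.3 include no atrophy, skull or lesion measure, so beating them does not separate delivered current from anatomy.

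At stake is the interpretation. A marker of who benefits from CT could be reported as a tDCS dose marker and could shape the computational target of the Exploratory Aim.

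**Working it through.** **Arm sizes.** Section 6.1 gives 80 participants in four Phase 1 conditions and 280 in Phase 2: 80 + 280 = 360, as stated. With the balanced blocks of Section 6.2, each Phase 1 arm has 80/4 = 20 and each Phase 2 CT arm 280/2 = 140. Each CT arm therefore has 20 + 140 = 160 if TC is dropped, before attrition. Section 6.18 gives no power figure for Aim 2 to reproduce.

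**Assumptions, none from the documents.** 40% responders; anatomy-current correlation a from 0.2 to 0.7; anatomy-gain correlation b from 0.1 to 0.4; one current feature; zero tDCS effect.

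**Step 1: association with no tDCS effect.** Current and gain then correlate at a × b in both arms. For a cut that leaves a proportion p = 0.40 as responders, the normal density at the cut is 0.386, and the responder-minus-non-responder difference in current is

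D = a·b × 0.386 / (0.4 × 0.6) = 1.61·a·b (SD units).

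The test statistic is centred near λ = D × √(160 × 0.24) = 6.20·D. The chance of two-sided significance at 0.05 is Φ(λ − 1.96) + Φ(−λ − 1.96).

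| a, b | D | λ | Formula | Simulated, active arm |
|---|---|---|---|---|
| 0.2, 0.1 | 0.03 | 0.20 | 5.5% | 5.3% |
| 0.5, 0.3 | 0.24 | 1.50 | 32% | 32% |
| 0.7, 0.4 | 0.45 | 2.79 | 80% | 81% |

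Simulated D in active and sham was 0.04 and 0.03, 0.24 and 0.24, and 0.45 and 0.46, so the sham arm shows the same pattern. The between-arm contrast of slopes (two-sided 0.05) was positive in about 5% of runs throughout.

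**Step 2: what a real effect looks like.** With a true 0.3 SD effect of current in the active arm and no confounding, the correlation is 0.3/√1.09 = 0.287 and D = 1.61 × 0.287 = 0.46 in active (0.00 in sham). That is as large as the most extreme confounded case, so the active arm alone cannot tell the two apart. The sham arm can.

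**Step 3: power of the contrast.** The standard error of the difference in slopes is √(2/160) = 0.112.

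- 0.2 SD: 0.2/0.112 = 1.79, Φ(1.79 − 1.96) = 43%.
- 0.3 SD: 0.3/0.112 = 2.68, Φ(2.68 − 1.96) = 76%.

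The one-arm responder association has about 50% and 83% (simulated). With 128 per arm (an assumed 20% attrition) the simulated contrast has 36% and 66%. With a five-feature out-of-sample score and 160 per arm it has 26% and 60%.

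**Step 4: what the contrast cannot show.** Let current have no effect, but let anatomy modify the response to tDCS by m SD through another route. The slopes then differ by a·m. For a = 0.5 and m = 0.3, 0.15/0.112 = 1.34, and Φ(1.34 − 1.96) = 27% at one-sided 0.025 (25% simulated). For a from 0.3 to 0.7 and m from 0.2 to 0.4, simulation gives 7.6% to 68%. The contrast removes prognostic confounding. It does not separate current from anatomy as an effect modifier.

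**The case against.** Much of the opposing case stands. Prediction needs no sham arm, and balanced accuracy is a prediction measure. Dose is partly a label, since Aim 1 defines computed current density as an estimate of it, and the text speaks of association and of possible precision dosing. Section 6.18 also states an aim of studying how current interacts with anatomy and lesions. What remains is that the same section draws conclusions about tDCS efficacy and builds a target from responders.

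Four stronger readings are tempting, and the documents do not support them.

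- *That the protocol itself establishes the confounding.* It makes it plausible only. H1.1 is a hypothesis, H1.2 compares models with and without lesions in the same person, and the main trial's HE.1, which links white matter abnormalities to poorer outcome, is exploratory. The models are described as T1-based, and it is not stated whether lesion-inclusive versions feed Aim 2.
- *That Aim 2 will be fitted in the active arm only.* This is an inference. Models cover all 360 and allocation will be available; the sham comparison is unspecified, not ruled out.
- *That the planned McNemar test is generally inflated.* Under the correlations above it succeeds in about 5% to 42% of simulated trials against an uninformative clinical score, but in about 0.1% to 10% if that score has its own 0.2 SD effect on gain. H2.1 and the Exploratory target do not depend on it.
- *That a positive arm contrast would justify the dose label.* Step 4 shows why it would not.

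**Conclusion.** The concern holds as a gap in attribution. As written, Section 6.18 cannot distinguish current that matters because of stimulation from current that marks who gains from CT or practice. The size cannot be fixed from the documents: the range of 5% to 81% rests on assumed correlations, a 40% responder share, one feature and 160 per arm, and it describes an association test that the plan does not name. At the weak end there is almost no inflation; the top needs both correlations at their highest assumed values.

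The consequence is limited. This is a secondary analysis, the target stays inside computational models, no participant is dosed from it, and the randomized comparison on the primary outcome is untouched. It merits consideration before unblinding.

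**What to change.** Before unblinding, add to Section 6.18:

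1. A responder definition (gain threshold and time point), the same in both arms.
2. Application of the same fitted current score to CT+sham participants as a negative control, with balanced accuracy reported by arm. Sham is 30 seconds of current against 20 minutes (Section 6.5), so it serves this purpose well.
3. One directional test, one-sided 0.025 with out-of-sample scores, of whether the score's association with continuous FCCS gain is larger in CT+tDCS than in CT+sham. In simulation with a five-feature score and no tDCS effect, a two-sided 0.05 version rejected in 7% to 9% of runs and the directional version in 1.7% to 2.9%.
4. An interpretation rule. A positive contrast is evidence that the association is specific to stimulation, not proof of a current-dose effect, because current is not randomised. A non-significant contrast is inconclusive.
5. A sensitivity analysis adding the anatomical measures already planned for Aim 1 and their interactions with arm.
6. In the Exploratory Aim, keep the planned target, show the CT+sham responders' current distribution beside it, and state that active-arm responders include people who gained from CT or practice. Do not gate features on significance: one test of a combined score cannot say which features are supported, and a gate would contradict treating a non-significant contrast as inconclusive.

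No new data are needed. The costs are analysis work and the lower power of the contrast shown in Step 3.
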